### 5.6.4 VORINOSTAT

Procedures for proper handling and disposal of vorinostat as cytotoxic drug should be employed. The drug should only be dispensed at Royal Free Hospital to those randomised to Arm B. Total number of doses is 10 x 400mg doses over 28 days with 4 x 100mg capsules taken every third day with food. Vorinostat will be dispensed to participants on PR week 08 day 1 (PR08-1) at the Royal Free Hospital at the participant's second vaccination visit. Participants will be required to bring their vorinostat to their clinic visit (at recruiting site) at PR week 08 day 3 (PR08-3). Participants will be required to take their first vorinostat dose in clinic. Ideally, Day 1 of vorinostat dosing will occur on a Wednesday to avoid study blood draws over the weekend. Dosing should be undertaken at the same time each day. Vorinostat must be kept at room temperature, 15°-30°C (59°-86°F). Vorinostat capsules if damaged or broken should not be used. Vorinostat capsules must not be opened or crushed. If vorinostat powder (within the capsule) comes into contact with skin or mucous membranes, the area must be washed immediately with plain water; participants should notify the site.

## 5.7 STOPPING DRUG EARLY

### 5.7.1 COMBINATION ART

Participants ceasing cART at any point on the study for toxicity or other reasons should be managed according to the BHIVA antiretroviral guidelines for adults. Participants choosing to stop cART cannot receive further vaccination or vorinostat if randomised to Arm B.

### 5.7.2 RALTEGRAVIR

Participants that cease raltegravir at any point on the study for toxicity or other reasons should be managed according to the BHIVA antiretroviral guidelines for adults. Ideally, an intra-class substitution is preferred i.e. with another integrase inhibitor such as dolutegravir, provided there is no contraindication to use. If, however, it is not possible to substitute another drug to replace raltegravir, they can continue with vaccination and vorinostat as per protocol if randomised to Arm B provided their HIV RNA remains <50copies/mL.

### 5.7.3 VACCINES

In the event of a severe local or systemic reaction to the first vaccination (ChAd) the following must be considered in regards to administration of the second vaccination (MVA).

1. The second vaccination must not be given if an anaphylactic reaction occurred after the first vaccine administration.
2. In the event of a severe local reaction **or** non-anaphylactic systemic reaction, the site should discuss with the RIVER Co-ordinating Centre team in the first instance who will then discuss with the IDMC for the RIVER study. Advice will be given on whether the second vaccination should be given.

If the participant does not receive the second vaccination for any reason, the participants should remain on cART and in follow-up for the study. Only participants who have received both doses of the vaccines (remain on cART and meet eligibility criteria see [Section 5.4](#)) can proceed to vorinostat dosing.

### 5.7.4 VORINOSTAT

In the event of a serious AE related to vorinostat the dosing will be terminated early. See below ([Section 5.8](#)) and in [Appendix II](#) for further guidance of toxicity management and dosing.

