### 5.8.1 VORINOSTAT TOXICITY MANAGEMENT

In the event of any vorinostat toxicity **Table 5** details actions that should be taken.

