**Table 5 Toxicity management during vorinostat dosing**

Toxicity	Grade	Vorinostat Dosing Action	Continuation
Non-haematological toxicity	Grade 1 or 2	No change unless due to impairment of QoL at discretion of Investigator (consider dose reduction as detailed below for Grade 2 toxicity)	Continue
Non-haematological toxicity	Grade 3 or 4	Cease treatment	Never
Anaemia, neutropenia or thrombocytopenia	Grade 1	No change	Continue
Neutropenia	Grade 2	Withhold vorinostat until returns to Grade $\leq 1$ .	If resolves to Grade $\leq 1$ , continue vorinostat at full dose. If on rechallenge recurs to Grade 2 or above, cease treatment. G-CSF is allowed at the clinician's discretion
Neutropenia	Grade 3 or 4	Cease treatment	
Febrile neutropenia	Grade 3 or 4	Cease treatment	
Anaemia or thrombocytopenia	Grade 2	Withhold vorinostat until returns to $\leq$ Grade 1	If resolves to $\leq$ Grade 1, continue vorinostat at full dose. If on rechallenge recurs to Grade 2 or above, cease treatment.
Anaemia or thrombocytopenia	Grade 3 or 4	Cease treatment	

Specific toxicity management in the setting of vorinostat dosing is provided in **Table 5** above. Grade 2 non-haematological toxicities, at the discretion of the treating clinician and with the agreement of the participant, can be managed with dose reduction of vorinostat to 300mg every third day. If the participant is intolerant of this reduced dose then the drug should be ceased all together, see **Section 5.7**.

All attempts must be made to avoid treatment interruptions; especially those for non-medical reasons e.g. 'drug holidays' or lost prescriptions. Treatment interruptions for medical reasons e.g. unable to have oral intake for whatever reason, are unavoidable and are permissible under this protocol as a protocol deviation. Every attempt should be made to limit the duration of treatment interruptions.

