**Table 6 Definitions**

TERM	DEFINITION
Adverse Event (AE)	Any untoward medical occurrence in a participant or clinical study subject to whom a medicinal product has been administered including occurrences that are not necessarily caused by or related to that product.
Adverse Reaction (AR)	Any untoward and unintended response to an investigational medicinal product related to any dose administered.
Unexpected Adverse Reaction (UAR)	An adverse reaction, the nature or severity of which is not consistent with the information about the medicinal product in question set out in the Summary of Product Characteristics (SmPC) or Investigator Brochure (IB) for that product.
Serious Adverse Event (SAE) or Serious Adverse Reaction (SAR) or Suspected Unexpected Serious Adverse Reaction (SUSAR)	Respectively any adverse event, adverse reaction or unexpected adverse reaction that: 
 
▪ Results in death
 
▪ Is life-threatening+++
 
▪ Requires hospitalisation or prolongation of existing hospitalisation§§§
 
▪ Results in persistent or significant disability or incapacity
 
▪ Consists of a congenital anomaly or birth defect
 
▪ Is another important medical condition****
 

+++ The term life-threatening in the definition of a serious event refers to an event in which the participant is at risk of death at the time of the event; it does not refer to an event that hypothetically might cause death if it were more severe, for example, a silent myocardial infarction.

§§§ Hospitalisation is defined as an inpatient admission, regardless of length of stay, even if the hospitalisation is a precautionary measure for continued observation. Hospitalisations for a pre-existing condition, that has not worsened or for an elective procedure do not constitute an SAE.

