\*\*\*\* Medical judgement should be exercised in deciding whether an AE or AR is serious in other situations. The following should also be considered serious: important AEs or ARs that are not immediately life-threatening or do not result in death or hospitalisation but may jeopardise the subject or may require intervention to prevent one of the other outcomes listed in the definition above; for example, a secondary malignancy, an allergic bronchospasm requiring intensive emergency treatment, seizures or blood dyscrasias that do not result in hospitalisation or development of drug dependency.

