#### 7.4.1.C CAUSALITY

The investigator must assess the causality of all serious events or reactions in relation to the study therapy using the definitions in [Table 7](#). There are five categories: unrelated, unlikely, possible, probable, and definitely related. If the causality assessment is unrelated or unlikely to be related, the

event is classified as an SAE. If the causality is assessed as possible, probable or definitely related, then the event is classified as an SAR.

If an SAE is considered to be related to study treatment and drug is stopped or the dose modified, refer to [Section 5.8](#).

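### For a Grade 1–2 adverse event that is serious and related to vorinostat, Section 5.7.4 and Table 5 give different dosing actions, and the protocol text does not say which prevails

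*Protocol*

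**What the plan says.** Section 5.7.4 acts on seriousness and relatedness: "In the event of a serious AE related to vorinostat the dosing will be terminated early". It mentions no grade. It then points to Section 5.8 and Appendix II for further guidance.

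Section 5.8.1 introduces Table 5 with the words "In the event of any vorinostat toxicity". Table 5 is organised by toxicity type and grade, and no row or note refers to seriousness:

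- Non-haematological, Grade 1 or 2: "No change unless due to impairment of QoL at discretion of Investigator", and dosing continues. For Grade 2, the table and the text below it allow a reduced dose.
- Anaemia, neutropenia or thrombocytopenia, Grade 1: no change, continue.
- Anaemia, neutropenia or thrombocytopenia, Grade 2: withhold; on recovery to Grade 1 or lower, "continue vorinostat at full dose. If on rechallenge recurs to Grade 2 or above, cease treatment".
- Grade 3 or 4, every row: cease.

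Section 7.4.1.B has serious and non-serious events graded on the same toxicity table, so grade and seriousness are separate attributes. Under the footnotes to Table 6, an inpatient admission makes an event serious "regardless of length of stay, even if the hospitalisation is a precautionary measure for continued observation". The examples of important medical events that should be considered serious include "seizures or blood dyscrasias that do not result in hospitalisation or development of drug dependency".

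Section 7.4.1.C carries a conditional cross-reference to Section 5.8: "If an SAE is considered to be related to study treatment and drug is stopped or the dose modified".

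**The concern.** One rule turns on seriousness and the other on grade. If the two attributes always moved together, nothing would follow. They do not, because a mild or moderate event can meet the protocol's definition of serious. A site facing such an event finds an instruction to end vorinostat in one section and, in the section it is then sent to, an instruction to continue or to withhold and resume.

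The stake is mainly participant safety. Section 1.1.2 says vorinostat is not licensed for HIV. Section 7.3.2 describes it as mutagenic in vitro, with an unknown malignancy risk even after short exposure. Whether someone is dosed again after a related serious event should not depend on which section was opened.

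The event types are foreseeable. Section 1.1.1.D reports dehydration as a serious drug-related experience in earlier cancer trials, and Section 5.14.3 names thrombocytopenia among the most common side effects.

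There is a smaller analytic stake. SAP Section 4.6 defines a per-protocol sensitivity analysis by whether vorinostat was stopped, and SAP Section 4.8 analyses treatment-modifying adverse events.

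**Working it through.** The plan states no figure on this point, so the check is a comparison of texts.

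**Step 1: can a related event be both serious and Grade 1–2?** Yes. Under Table 6 a short admission for observation makes an event serious whatever its grade, and a blood dyscrasia without admission may be judged serious. The second route needs medical judgement: the footnote speaks of events that may jeopardise the participant or need intervention to prevent a worse outcome. A Grade 2 count need not qualify.

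**Step 2: compare the two rules case by case.**

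| Event related to vorinostat | Section 5.7.4 | Table 5 | Agree? |
|---|---|---|---|
| Serious, Grade 3–4, any type | End dosing | Cease | Yes |
| Serious, Grade 1–2, non-haematological | End dosing | Continue; reduction possible at Grade 2 | No |
| Serious, Grade 1 cytopenia | End dosing | Continue | No |
| Serious, Grade 2 cytopenia | End dosing | Withhold, then resume at full dose on recovery | No |
| Not serious, any grade | Does not apply | Applies | No conflict |

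SAP Section 2.4 has every Grade 4 event reported as an SAE. The rules therefore always overlap at Grade 4 when the event is related, and there they agree.

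**Step 3: is precedence stated?** Not in the text available. Section 5.7.4 does not say that it overrides Table 5, and it sends the site to Section 5.8 for dosing guidance. Section 5.8.1 does not exempt serious events. Table 5 contains its own permanent stops, so a site could take it as complete. Appendix II was not available to check.

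**Step 4: what does Section 7.4.1.C add?** It allows for a related SAE after which the drug is stopped or its dose modified, and points to Section 5.8. A modified dose does not sit easily with an unconditional stop. This is supporting evidence only (see the objection).

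**Step 5: which analyses could change?** The SAP's per-protocol set excludes any temporary or complete stop of vorinostat.

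- Grade 2 cytopenia: withholding is a temporary stop and termination a complete one. The participant is excluded either way, and I assume that either would count as treatment-modifying.
- Grade 1–2 non-haematological event or Grade 1 cytopenia, continued unchanged: under Section 5.7.4 the participant is excluded and the event counts as treatment-modifying. Under Table 5 neither follows.
- Grade 2 non-haematological event, dose reduced: reduction is not among the stops that the SAP lists, so the per-protocol set can differ. I assume that the event counts as treatment-modifying either way.

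For scale, the 52 to 60 participants in Section 9.3 at 1:1 give 52/2 = 26 to 60/2 = 30 in Arm B, so one participant is 1/30 = 3.3% to 1/26 = 3.8% of the arm. The intention-to-treat population for the primary analysis is unaffected.

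**The case against.** The best counter-argument is that the texts can be read together. Section 5.7.4 is the specific rule for serious related events, and Table 5 handles whatever that rule has not already stopped. The reading is coherent, and Appendix II may even state it. But neither section says so, and Section 5.7.4 refers the site onward to guidance that applies to any vorinostat toxicity. The objection shows how the gap could be closed, not that it is closed.

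Three stronger readings are tempting and are not supported:

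- A reader might infer a conflict for every related serious event. Table 5 says cease in each Grade 3–4 row, so the conflict is confined to Grade 1–2.
- A reader might take Section 7.4.1.C as permission to continue, reduce or rechallenge. It is only a cross-reference that applies if drug was stopped or modified. It also concerns study treatment in general, which under Section 7.1.1 includes raltegravir, the ART backbone and both vaccines.
- A reader might express the conflict as a large difference in exposure. With 10 planned doses, stopping after dose k against continuing unchanged gives a ratio of 10/k: 5 after dose 2, 2 after dose 5, 1.1 after dose 9. The figure depends on the chosen k and does not measure the trial's risk.

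It is also fair to say that SAEs are notified within 24 hours (Section 7.4.1.E) and that medically qualified staff or the chief investigator review every report (Section 7.5). Divergent handling would therefore probably be seen centrally. That limits the harm but does not tell the site what to do when the event occurs.

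**Conclusion.** The concern holds within narrow limits. For an event that is serious, related to vorinostat and of Grade 1–2, Section 5.7.4 and Table 5 read literally give different dosing actions, and no available text ranks them. At Grade 3–4 they agree.

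The number of participants affected cannot be estimated from the documents and may be small. The consequence is chiefly for participant safety. The analytic effect is limited to sensitivity and safety summaries, and to low-grade serious events that Table 5 lets continue without a stop.

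The conclusion rests on two assumptions: that Appendix II does not already settle precedence, and that low-grade events will sometimes meet the protocol's definition of serious. No view is taken on which dosing rule is right.

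**What to change.** Reconcile Section 5.7.4 with Table 5, and with Appendix II if it bears on the point. One added line should state which rule governs an event that is serious, related to vorinostat and of Grade 1–2. Then check that the wording of Section 7.4.1.C is consistent with that line. The choice of rule belongs to the sponsor.

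The cost is a short wording change at the next amendment and a note to sites. No new data, visits or analyses are needed.

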## 5.8 DOSE MODIFICATIONS, INTERRUPTIONS & DISCONTINUATIONS

Toxicity will be managed in all randomised groups according to standard clinical practice. Blood tests additional to those described in the study schedule may be requested at any time for clinical management of the participant.

### 5.8.1 VORINOSTAT TOXICITY MANAGEMENT

In the event of any vorinostat toxicity **Table 5** details actions that should be taken.

**Table 5 Toxicity management during vorinostat dosing**

Toxicity	Grade	Vorinostat Dosing Action	Continuation
Non-haematological toxicity	Grade 1 or 2	No change unless due to impairment of QoL at discretion of Investigator (consider dose reduction as detailed below for Grade 2 toxicity)	Continue
Non-haematological toxicity	Grade 3 or 4	Cease treatment	Never
Anaemia, neutropenia or thrombocytopenia	Grade 1	No change	Continue
Neutropenia	Grade 2	Withhold vorinostat until returns to Grade $\leq 1$ .	If resolves to Grade $\leq 1$ , continue vorinostat at full dose. If on rechallenge recurs to Grade 2 or above, cease treatment. G-CSF is allowed at the clinician's discretion
Neutropenia	Grade 3 or 4	Cease treatment	
Febrile neutropenia	Grade 3 or 4	Cease treatment	
Anaemia or thrombocytopenia	Grade 2	Withhold vorinostat until returns to $\leq$ Grade 1	If resolves to $\leq$ Grade 1, continue vorinostat at full dose. If on rechallenge recurs to Grade 2 or above, cease treatment.
Anaemia or thrombocytopenia	Grade 3 or 4	Cease treatment	

Specific toxicity management in the setting of vorinostat dosing is provided in **Table 5** above. Grade 2 non-haematological toxicities, at the discretion of the treating clinician and with the agreement of the participant, can be managed with dose reduction of vorinostat to 300mg every third day. If the participant is intolerant of this reduced dose then the drug should be ceased all together, see **Section 5.7**.

All attempts must be made to avoid treatment interruptions; especially those for non-medical reasons e.g. 'drug holidays' or lost prescriptions. Treatment interruptions for medical reasons e.g. unable to have oral intake for whatever reason, are unavoidable and are permissible under this protocol as a protocol deviation. Every attempt should be made to limit the duration of treatment interruptions.

#### 5.8.1.A SPECIFIC GUIDELINES FOR MANAGEMENT OF EXPECTED TOXICITIES:

- **Diarrhoea** – management with loperamide is strongly encouraged.
- **Dehydration** – encourage anti-emetics and anti-diarrhoeals as appropriate; encourage drinking of at least 2L fluid per day. Rehydration solutions are also encouraged as appropriate.
- **Nausea and vomiting** – aggressive management is encouraged.
- **Hyperglycaemia** – monitor blood glucose closely, treat with hypoglycaemic agents as appropriate.
- **Electrolyte disturbance** – replace potassium, calcium and magnesium as appropriate, as guided by regular blood electrolyte tests.
- **Venous thromboembolism** – monitor closely for signs and symptoms and investigate if there is suspicion of embolic event or venous thrombosis
- **QTc prolongation** – aggressively manage electrolyte disturbances.
- **Hematologic toxicities:**
  - **Anaemia** – transfuse as per institutional guidelines. Erythropoietin is allowed on-study as per prescribing guidelines.
  - **Neutropenia** – G-CSF is allowed on-study at investigator discretion.
  - **Thrombocytopenia** - Platelet transfusions should be administered in the following situations:
    - Platelets  $<10 \times 10^9/L$ .
    - Platelets  $<20 \times 10^9/L$  with fever  $\geq 38.5^\circ C$  due to infection or presumed infection (at discretion of treating clinician).
    - Platelets  $<20 \times 10^9/L$  with clinically significant bleeding (at discretion of treating clinician).
    - Platelets  $<50 \times 10^9/L$  in participants having invasive procedures (at discretion of treating clinician).

If the participant is intolerant of the 300mg every third day dose, then the drug should be ceased all together, see [Section 5.7](#).

#### 5.8.1.B VIROLOGICAL REBOUND

If a significant increase in viral replication occurs at any time on study (while on or off vorinostat), the Trial Physician will be informed, the participant managed according to current guidelines and continuation in the trial will be managed on a case by case basis. Participants must have HIV RNA  $<50$  copies/mL ( $<200$  copies/mL Taqman Roche 2.0 assay) to be eligible for randomisation.

## 5.9 OVERDOSE OF TRIAL MEDICATION

All participants should be counselled about the importance of taking the medications as prescribed. It is particularly important that participants understand how many tablets of which type they are taking. Participants must be told to contact their clinic immediately if they take too many tablets. In the event of overdose of study medication, all appropriate medical care will be given and regular tests will be carried out to ensure safety.

## 5.10 PROTOCOL TREATMENT DISCONTINUATION

In consenting to the study, participants are consenting to study treatment, study follow-up and data collection. However, an individual participant may stop treatment early or be stopped early for any of the following reasons:

- Unacceptable toxicity or adverse event.
- Intercurrent illness that prevents further treatment.
- Development of malignancy.
- Any change in the participant's condition that, in the opinion of the clinician, justifies treatment discontinuation. Clinicians should avoid interruption of a suppressive ART regimen unless this is unavoidable.
- Inadequate compliance with the protocol treatment in the judgement of the treating physician.
- Withdrawal of consent for study intervention medication by the participant.

As the participant's participation in the study is entirely voluntary, they may choose to discontinue the study treatment at any time without penalty or loss of benefits to which they are otherwise entitled. Although the participant is not required to give a reason for discontinuing their study treatment, a reasonable effort should be made to establish this reason while fully respecting the participant's rights.

Participants should remain in the study for the purpose of follow-up and data analysis (unless the participant withdraws their consent from all stages of the study). If a participant is withdrawn from follow-up, refer to [Section 6.5](#).

Data will be kept and included for participants who stop follow-up early.

## 5.11 ACCOUNTABILITY & UNUSED DRUGS

Investigational Medicinal Product (IMP) will be centrally packed and distributed as described in [Section 5.1](#). Supplies of raltegravir will be sent to the hospital pharmacy at each of the participating sites. The hospital pharmacy will document receipt of supplies and destruction of any raltegravir returned by a participant.

Supplies of raltegravir will be dispensed to a participant from the site at which they were recruited. Vaccines and vorinostat will be dispensed to participants in Arm B at their visits to Royal Free Hospital. Unused vaccine and/or vorinostat will be returned to the study pharmacy and entered onto the accountability log. Vorinostat will be handled and destroyed as per the requirements of a chemotherapy (anti-cancer) drug. Study vaccines will be disposed of as Genetically Modified Organism (GMO) waste by autoclaving and usual disposal, in accordance with current standard UK practice.

IMP accountability will be maintained and monitored by site staff and RIVER Co-ordinating Centre respectively according to the RIVER working practices and pharmacies will be asked to maintain records of any returned IMP. At the end of the study all non-dispensed IMP will be checked against the inventory before disposal. Disposal of IMP should not be carried out without approval of the RIVER Trial Manager and should be carried out according to local pharmacy guidelines and applicable regulations. Documentation of disposal will be provided to RIVER Co-ordinating Centre.

